## **9.0 Ethics**

### **9.1 Independent Ethics Committee (IEC) or Institutional Review Board (IRB)**

Good Clinical Practice (GCP) requires that the clinical protocol, any protocol amendments, the Investigator's Brochure, the informed consent and all other forms of subject information related to the study (e.g., advertisements used to recruit subjects) and any other necessary documents be reviewed by an Independent Ethics Committee (IEC)/Institutional Review Board (IRB). The IEC/IRB will review the ethical, scientific and medical appropriateness of the study before it is conducted. IEC/IRB approval of the

protocol, informed consent and subject information and/or advertising, as relevant, will be obtained prior to the authorization of drug shipment to a study site.

Any amendments to the protocol will require IEC/IRB approval prior to implementation of any changes made to the study design. The investigator will be required to submit, maintain and archive study essential documents according to ICH GCP and all other applicable regulatory requirements.

Any serious adverse events that meet the reporting criteria, as dictated by local regulations, will be reported to both responsible Ethics Committees and Regulatory Agencies, as required by local regulations. During the conduct of the study, the investigator should promptly provide written reports (e.g., ICH Expedited Reports, and any additional reports required by local regulations) to the IEC/IRB of any changes that affect the conduct of the study and/or increase the risk to subjects. Written documentation of the submission to the IEC/IRB should also be provided to AbbVie.

## **9.2 Ethical Conduct of the Study**

The study will be conducted in accordance with the protocol, International Conference on Harmonization (ICH) guidelines, applicable regulations and guidelines governing clinical study conduct and the ethical principles that have their origin in the Declaration of Helsinki. Responsibilities of the clinical investigator are specified in [Appendix A](#).

## **9.3 Subject Information and Consent**

The investigator or his/her representative will explain the nature of the study to the subject, and answer all questions regarding this study. Prior to any study-related screening procedures being performed on the subject, the informed consent statement will be reviewed and signed and dated by the subject, the person who administered the informed consent, and any other signatories according to local requirements. A copy of the informed consent form will be given to the subject and the original will be placed in the subject's medical record. An entry must also be made in the subject's dated source

documents to confirm that informed consent was obtained prior to any study-related procedures and that the subject received a signed copy.

Information regarding incentives for subjects and information regarding provisions for treating and/or compensating subjects who are harmed as a consequence of participation in the study can be found in the informed consent form.

## **10.0                   Source Documents and Case Report Form Completion**

### **10.1                   Source Documents**

Source documents are defined as original documents, data and records. This may include hospital records, clinical and office charts, laboratory data/information, subjects' diaries or evaluation checklists, pharmacy dispensing and other records, recorded data from automated instruments, microfiches, photographic negatives, microfilm or magnetic media, and/or x-rays. Data collected during this study must be recorded on the appropriate source documents. The Investigator Awareness Date (SAE CRF) may serve as the source for this data point. This adverse event data point required for eCRF completion can be entered directly in the eCRF.

The investigator(s)/institution(s) will permit study-related monitoring, audits, IEC/IRB review, and regulatory inspection(s), providing direct access to source data documents.

### **10.2                   Case Report Forms**

Case report forms (CRF) must be completed for each subject screened/enrolled in this study. These forms will be used to transmit information collected during the study to AbbVie and regulatory authorities, as applicable. The CRF data for this study are being collected with an electronic data capture (EDC) system called Rave® provided by the technology vendor Medidata Solutions Incorporated, NY, USA. The EDC system and the study-specific electronic case report forms (eCRFs) will comply with Title 21 CFR Part 11. The documentation related to the validation of the EDC system is available

through the vendor, Medidata, while the validation of the study-specific eCRFs will be conducted by AbbVie and will be maintained in the Trial Master File at AbbVie.

The investigator will document subject data in his/her own subject files. These subject files will serve as source data for the study. All eCRF data required by this protocol will be recorded by investigative site personnel in the EDC system. All data entered into the eCRF will be supported by source documentation.

The investigator or an authorized member of the investigator's staff will make any necessary corrections to the eCRF. All change information, including the date and person performing the corrections, will be available via the audit trail, which is part of the EDC system. For any correction, a reason for the alteration will be provided. The eCRFs will be reviewed periodically for completeness, legibility, and acceptability by AbbVie personnel (or their representatives). AbbVie (or their representatives) will also be allowed access to all source documents pertinent to the study in order to verify eCRF entries. The principal investigator will review the eCRFs for completeness and accuracy and provide his or her electronic signature and date to eCRFs as evidence thereof.

Medidata will provide access to the EDC system for the duration of the trial through a password-protected method of internet access. Such access will be removed from investigator sites at the end of the site's participation in the study. Data from the EDC system will be archived on appropriate data media (CD-ROM, etc.) and provided to the investigator at that time as a durable record of the site's eCRF data. It will be possible for the investigator to make paper printouts from that media.

Patient Reported Outcome (PRO) data must be completed for each subject screened/enrolled in this study. These data are being collected with an Electronic Patient Reported Outcome (ePRO) system called Trialmax, provided by the technology vendor CRF Health of Plymouth Meeting, PA, USA. The ePRO system is in compliance with Title 21 CFR Part 11. The documentation related to the system validation of the ePRO system is available through the vendor, CRF Health, while the user acceptance testing of the study-specific PRO design will be conducted and maintained at AbbVie.

The subject will be entering the data on an electronic device; these data will be uploaded to a server. The data on the server will be considered source, and maintained and managed by CRF Health.

Internet access to the ePRO data will be provided by CRF Health for the duration of the study. This access will be available for the duration of the study to the site investigator, as well as delegated personnel. Such access will be removed from investigator sites following the receipt of the study archive. Data from the ePRO system will be archived on appropriate data media (CD-ROM, etc.) and provided to the investigator at that time as a durable record of the site's ePRO data. It will be possible for the investigator to make paper print-outs from that media.

The ePRO data will be collected by the following methods:

**Tablet Based**

- The instruments/scales will be collected electronically via a Tablet/Laptop device into which the patient will directly enter the required pieces of information. The electronic device will be programmed to allow data entry for only the visits specified in the protocol and will not allow for subjects to complete more than one of the same assessment at any one visit. All data entered on the device will be immediately stored to the device itself and automatically uploaded to a central server administrated by CRF Health. The Investigator and delegated staff will be able to access all uploaded patient entered data via a password protected website, up until the generation, receipt and confirmation of the study archive.

## **11.0 Data Quality Assurance**

Computer logic and manual checks will be created to identify items such as inconsistent study dates. Any necessary corrections will be made to the eCRF.

Prior to the initiation of the study, a meeting will be held with AbbVie personnel, the investigators and appropriate site personnel. This meeting will include a detailed

discussion of the protocol, performance of study procedures, eCRF, Subject Questionnaires, and Subject Diary completion, and specimen collection methods. The AbbVie monitors will monitor each site throughout the study.

All data hand entered in the database will be verified at AbbVie. Any discrepancies will be reviewed. After completion of the entry process, computer logic checks will be run to check for such items as inconsistent study dates. Any necessary corrections will be made to the eCRF.

The data from the central laboratory analyses will be electronically transferred from the central laboratory to the study database.

## **12.0      Use of Information**

All information concerning specify study drug and AbbVie operations, such as AbbVie patent applications, formulas, manufacturing processes, basic scientific data, or formulation information, supplied by AbbVie and not previously published is considered confidential information. The information developed during the conduct of this clinical study is also considered confidential and will be used by AbbVie in connection with the development of specify study drug. This information may be disclosed as deemed necessary by AbbVie to other clinical investigators, other pharmaceutical companies, and to governmental agencies. To allow for the use of the information derived from this clinical study and to ensure complete and thorough analysis, the investigator is obligated to provide AbbVie with complete test results and all data developed in this study and to provide direct access to source data/documents for trial-related monitoring, audits, IEC/IRB review and regulatory inspection. This confidential information shall remain the sole property of AbbVie, shall not be disclosed to others without the written consent of AbbVie, and shall not be used except in the performance of this study. The investigator will maintain a confidential subject identification code list of all subjects enrolled in the study (by name and subject number). This list will be maintained at the site and will not be retrieved by AbbVie.

## **13.0                   Completion of the Study**

The investigator will conduct the study in compliance with the protocol and complete the study within the timeframe specified in the contract between the investigator and AbbVie. Continuation of this study beyond this date must be mutually agreed upon in writing by both the investigator and AbbVie. The investigator will forward a copy of this final report to the IEC/IRB following conclusion of the study and will forward a copy of this report to AbbVie or their representative.

The investigator must submit, maintain, and archive any records related to the study according to ICH GCP and all other applicable regulatory requirements. If the investigator is not able to retain the records, he/she must notify AbbVie to arrange alternative archiving options.

AbbVie will select the signatory investigator from the investigators who participate in the study. Selection criteria for this investigator will include level of participation as well as significant knowledge of the clinical research, investigational drug and study protocol. The signatory investigator for the study will review and sign the final study report in accordance with the European Agency for the Evaluation of Medicinal Products (EMEA) Guidance on Investigator's Signature for Study Reports.

The end-of-study is defined as the date of the last subject's last visit, Week 24/Early Termination Visit, see [Appendix C](#).

---

## **Appendix A. Responsibilities of the Clinical Investigator**

Clinical research studies sponsored by AbbVie are subject to the Good Clinical Practices (GCP) and local regulations and guidelines governing the study at the site location. In signing the Investigator Agreement in Section 14.0 of this protocol, the investigator is agreeing to the following:

1. Conducting the study in accordance with the relevant, current protocol, making changes in a protocol only after notifying AbbVie, except when necessary to protect the safety, rights or welfare of subjects.
2. Personally conducting or supervising the described investigation(s).
3. Informing all subjects, or persons used as controls, that the drugs are being used for investigational purposes and complying with the requirements relating to informed consent and ethics committees (e.g., independent ethics committee [IEC] or institutional review board [IRB]) review and approval of the protocol and amendments.
4. Reporting adverse experiences that occur in the course of the investigation(s) to AbbVie and the site director.
5. Reading the information in the Investigator's Brochure/safety material provided, including the instructions for use and the potential risks and side effects of the investigational product(s).
6. Informing all associates, colleagues, and employees assisting in the conduct of the study about their obligations in meeting the above commitments.
7. Maintaining adequate and accurate records of the conduct of the study, making those records available for inspection by representatives of AbbVie and/or the appropriate regulatory agency, and retaining all study-related documents until notification from AbbVie.
8. Maintaining records demonstrating that an ethics committee reviewed and approved the initial clinical investigation and all amendments.

9. Reporting promptly, all changes in the research activity and all unanticipated problems involving risks to human subjects or others, to the appropriate individuals (e.g., coordinating investigator, institution director) and/or directly to the ethics committees and AbbVie.
10. Following the protocol and not make any changes in the research without ethics committee approval, except where necessary to eliminate apparent immediate hazards to human subjects.
11. Not disclosing the treatment codes or any patient information to the blinded efficacy assessor.

Risankizumab  
M16-178 Protocol Amendment 3  
EudraCT 2016-003718-28

---

### Appendix C. Study Activities

Activity	Screening -30 to -1	Week 0/ Baseline	Week 4	Week 8	Week 12	Week 16	Week 20	Week 24/ET a	Week 31 Follow-Up Call b
Day	-30 to -1	Day 1	Day 29	Day 57	Day 85	Day 113	Day 141	Day 169	Day 218
Informed Consent	X								
Medical/Surgical History	X	X c							
Alcohol and Nicotine Use	X	X							
Pregnancy Tests d u = urine, s = serum	X(s)	X(u)	X(u)	X(u)	X(u)	X(u)	X(u)	X(u)	X(u)
Physical Exam c = complete, t = targeted	X(c)	X(c)	X(t)	X(t)	X(t)	X(c)	X(t)	X(c)	X(c)
Vital Signs e	X	X	X	X	X	X	X	X	X
Safety Laboratory Testing f c = complete, t = targeted	X(c)	X(c)	X(t)	X(c)	X(t)	X(c)	X(t)	X(c)	X(c)
Urinalysis	X	X	X	X	X	X	X	X	X
CASPAR Assessment	X								
FSH g	X								
PASI/% BSA Involvement	X	X	X	X	X	X	X	X	X
Assess Concomitant Medications	X	X	X	X	X	X	X	X	X
12 Lead ECG	X								
Infection Screening h	X								
Dispense Subject Diary i		X	X	X	X	X	X	X	X

Activity	Screening -30 to -1	Week 0/ Baseline	Week 4	Week 8	Week 12	Week 16	Week 20	Week 24/ET a	Week 31 Follow-Up Call b
Day	-30 to -1	Day 1	Day 29	Day 57	Day 85	Day 113	Day 141	Day 169	Day 218
DLQ j	X	X			X			X	
Randomization		X							
Risankizumab Administration k	X	X			X				
FUMADERM ® Dispensation l	X	X	X	X	X	X	X	X	
Blood Sampling for PK m		X	X			X	X	X	
Blood Sampling for ADA Assay m		X	X			X	X	X	
Subject Diary Review	X	X	X	X	X	X	X	X	
Monitor Adverse Events	X	X	X	X	X	X	X	X	
PPASI/PSI/NAPPA-CLIN j	X				X			X	
SPGA	X	X	X	X	X	X	X	X	
PSS j	X				X			X	
Monitor Compliance j	X	X	X	X	X	X	X	X	
Short Form SF-36 j	X				X			X	
Patient Benefit Index (PBI) j	X				X			X	
HADS j	X				X			X	
PtGA j	X				X			X	
EQ-5D-5L j	X				X			X	

a. Subjects that discontinue the study prior to the end of the study will have an Early Termination visit within 2 weeks after the decision to discontinue.

- b. Subjects that discontinue the study prior to the end of the study will have a follow-up phone call within 15 weeks after the last dose of FUMADERM® provided as study medication for collection of safety data. Subjects that elect to enroll into a separate extension study will not require the Week 31 Follow-Up phone call as part of this trial.
- c. Update history.
- d. Serum pregnancy test in all women at screening and if the urine pregnancy test is positive at any other visit. Urine pregnancy tests are to be performed in all women of child bearing potential prior to administration of study drug at all dosing visits.
- e. Height and weight will be measured at the Screening Visit only (with shoes off).
- f. Targeted laboratory samples should be limited to CBC with differential count (hematology), serum creatinine (substrates) and ALT, AST, gamma-GT and AP (enzymes).
- g. (FSH) To be done at Screening in all women aged ≤ 55 years with no menses for 12 or more months without an alternative medical cause.
- h. Infection screening consists of Hepatitis B Surface Antigen (qualitative), Hepatitis B Surface Antibody (qualitative), Total Hepatitis B Core Antibodies (qualitative), Hepatitis B Virus DNA (quantitative) reflex, Hepatitis C Virus RNA (quantitative) reflex, HIV-1 and HIV-2 Antibody (qualitative), PPD/QuantiFERON-TB.
- i. For FUMADERM® INITIAL and FUMADERM® provided as study medication only.
- j. Prior to other procedures.
- k. SC risankizumab 150 mg at Week 0/Day 1, Week 4 and Week 16. Risankizumab will be administered at the study site by authorized site personnel (e.g., study nurse) after all study procedures have been completed.
- l. Oral FUMADERM® daily starting at Week 0/Day 1 and until Week 24 (the last dose will be in the morning of the day of Week 24 visit). FUMADERM® INITIAL starting at Week 0/Day 1 until Week 2 and FUMADERM® starting at Week 3, both at starting dose of 1 tablet per day, followed by a dose increase of one tablet per week, depending on efficacy response and tolerability. The maximum dose of FUMADERM® of 6 tablets per day should not be exceeded.
- m. PK and ADA samples are collected only from the subjects receiving risankizumab.

---

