### **Treatment Period**

This period will begin at the Week 0/Day 1 (Baseline) Visit and will end at the Week 24/Early Termination (ET) Visit. At the Baseline Visit, subjects who meet all the inclusion criteria and none of the exclusion criteria described in Section [5.2](#) will be enrolled into the study and randomized to open-label treatment. During this period of the study, subjects will visit the site at Week 0 (Day 1/Baseline), Week 4, Week 8, Week 12, Week 16, Week 20 and Week 24/ET. A  $\pm$  4 day window is permitted around scheduled study visits. If any visit has to be rescheduled, subsequent visits should follow the original visit date schedule. Visits should take place on the same day of the week as much as possible. At the Week 24 visit, subjects who have completed the study will be offered the opportunity to participate in a separate extension study. For subjects that do not elect to enroll into the extension study, a follow-up phone call will be performed at Week 31.

Safety data will be collected throughout the treatment period and up to 15 weeks after the last dose of risankizumab and/or 7 weeks after the last dose of FUMADERM® provided as study medication in this study. Subjects may discontinue study drug treatment at any time during study participation. Subjects that discontinue the study prior to Week 24 will have an ET visit and complete the procedures outlined in [Appendix C](#) within 2 weeks

[figure not shown]
after the decision to discontinue and preferably prior to the administration of any new therapies.

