### **Follow-Up Period**

Subjects will have a follow-up phone call at approximately Week 31 (approximately 15 weeks after the last dose of risankizumab and 7 weeks after the last dose of FUMADERM® provided as study medication) with the exception of those subjects that elect to enroll into the extension study. All follow-up phone call procedures are noted in [Appendix C](#).

A schematic of the study design is shown below in [Figure 2](#).

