If, during the course of study drug administration, the subject prematurely discontinues study drug use, the procedures outlined for the Early Termination Visit must be completed within 2 weeks after the decision to discontinue, and preferably prior to the initiation of another therapy. However, these procedures should not interfere with the initiation of any new treatments or therapeutic modalities that the Investigator feels are necessary to treat the subject's condition. Following discontinuation of the study drug, the subject will be treated in accordance with the Investigator's best clinical judgment.

A final telephone call will occur for all subjects who do not roll over into the extension study, approximately 15 weeks after the last dose of risankizumab and 7 weeks after the last dose of FUMADERM®, provided as study medication, to determine the status of any ongoing AEs/SAEs or the occurrence of any new AEs/SAEs.

All attempts must be made to determine the date of the last study drug dose and the primary reason for early termination. The information will be recorded on the appropriate eCRF page.

For subjects that are considered lost to follow-up, reasonable attempts must be made to obtain information on the final status of the subject. At a minimum, two phone calls must be made and one certified letter must be sent and documented in the subject's source documentation.

Subjects who discontinue the study prematurely will not be replaced.

Subjects are considered study completers if they have completed the Week 24 visit.

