### **6.1.4 Adverse Event Collection Period**

All adverse events reported from the time of study drug administration until 15 weeks following discontinuation of risankizumab and 7 weeks following discontinuation of FUMADERM® (provided as study medication) administration have elapsed will be

collected, whether solicited or spontaneously reported by the subject. In addition, serious adverse events and protocol-related non-serious adverse events will be collected from the time the subject signed the study-specific informed consent.

Adverse event information will be collected as shown in [Figure 3](#).

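### Appendix C footnote b times the safety call for early discontinuers differently from Sections 5.1 and 5.4.1, and gives no time for risankizumab

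*Protocol*

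**What the plan says.** **Schedule.** Appendix C, footnote b, is attached to the Week 31 follow-up call. It begins "Subjects that discontinue the study prior to the end of the study will have a follow-up phone call", with no restriction by arm, and sets the time as "will have a follow-up phone call within 15 weeks after the last dose of FUMADERM® provided as study medication". It gives no interval for risankizumab and does not mention 7 weeks. It releases only subjects who enter the extension study.

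**Body text on the call.** Section 5.1 (Follow-Up Period) places the call at about Week 31, explained as "approximately 15 weeks after the last dose of risankizumab and 7 weeks after the last dose of FUMADERM® provided as study medication". Section 5.4.1 states "A final telephone call will occur for all subjects who do not roll over into the extension study", timed "approximately 15 weeks after the last dose of risankizumab and 7 weeks after the last dose of FUMADERM®, provided as study medication". Subjects who stop early are therefore included.

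**Body text on safety data collection.** Section 5.1 (Treatment Period) collects safety data "up to 15 weeks after the last dose of risankizumab and/or 7 weeks after the last dose of FUMADERM". Section 6.1.4 collects adverse events "until 15 weeks following discontinuation of risankizumab and 7 weeks following discontinuation of FUMADERM". These two places set a collection period, not a call time.

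**Analysis.** Protocol 8.1.5 and SAP 11.2.1 define treatment-emergent events by onset up to 105 days after the last risankizumab dose or 7 days after the last FUMADERM dose, with 49 days for FUMADERM in a sensitivity analysis. For rates per 100 patient-years, SAP 11.2.1 counts exposure as last dose minus first dose plus 105 days (risankizumab) or plus 7 or 49 days (FUMADERM).

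**The concern.** A site cannot simply set the appendix aside in favour of the body text, because the body text sends it there: Section 5.1 refers to Appendix C for the call procedures, and Section 5.3.1.1 refers to it for study procedures generally. Nor is the footnote an obvious slip to someone reading it alone, since inclusion criterion 7 also uses 15 weeks after FUMADERM, for contraception.

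For a subject who stops early, the call is the last scheduled contact in this study after the early termination visit, which is due within 2 weeks of the decision to stop. If the call comes before the analysis window closes, later events may go unrecorded while the SAP still credits the whole window as exposure. That would lower the estimated event rate in whichever arm it happened. The subjects concerned may have stopped because of adverse events, so uneven ascertainment among them matters for the safety comparison.

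**Working it through.** **Inputs.** Last scheduled risankizumab dose: Week 16, Day 113. Last scheduled FUMADERM dose: Week 24, Day 169. Call: Week 31, Day 218 (all Appendix C). Body-text intervals: 15 weeks = 105 days and 7 weeks = 49 days. Footnote b: up to 15 weeks = 105 days after FUMADERM.

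**Step 1. Reproduce the scheduled call.**
- Week 31: 31 × 7 + 1 = Day 218.
- Risankizumab, body text: 113 + 105 = Day 218.
- FUMADERM, body text: 169 + 49 = Day 218.
- Footnote b's FUMADERM interval from the same last dose: 169 + 105 = Day 274, which is Week 39 and 274 − 218 = 56 days later.

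The Week 31 call follows exactly from the body-text intervals in both arms and does not follow from the footnote's limit.

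**Step 2. Apply both texts to early discontinuers.**

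| Last dose | Section 5.4.1 | Footnote b |
|---|---|---|
| FUMADERM, Day 29 | about 29 + 49 = Day 78 | any time to 29 + 105 = Day 134 |
| FUMADERM, Day 85 | about 85 + 49 = Day 134 | any time to 85 + 105 = Day 190 |
| Risankizumab, Day 29 | about 29 + 105 = Day 134 | no time given |

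For FUMADERM the outer limits always differ by 105 − 49 = 56 days (8 weeks).

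**Step 3. What each departure does to the analysis.**
- *Early FUMADERM call.* A call 14 days after the last dose satisfies the footnote. It leaves 49 − 14 = 35 of the 49 days in the sensitivity window with no later scheduled contact. For a subject dosed from Day 1 to Day 29, the SAP credits (29 − 1) + 49 = 77 days of exposure, so those 35 days are 35/77 = 45% of that subject's credited time.
- *Late FUMADERM call.* A call between Day +49 and Day +105 loses none of the 49-day window. It runs past the collection period in Section 6.1.4.
- *Risankizumab.* The 105 days are credited whenever the call is made, and the footnote does not say when that is.
- *Primary FUMADERM window.* It closes at Day +7 and does not depend on a call at 7 weeks.

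**The case against.** The strongest answer is that the protocol as a whole is clear. The pairing of 15 and 7 weeks appears in four places in the body text and reproduces Day 218 in both arms, so the footnote may simply have lost some words. The analysis windows are defined by onset date and are unambiguous. An early call would breach Section 5.4.1, and Section 6.1.4 requires collection for the full period, including spontaneous reports, whenever the call is made.

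Much of this stands, and it rules out several stronger readings that a reader might draw:

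- *Risankizumab stoppers get no call.* Not supported. Footnote b covers both arms, and Section 5.4.1 gives them a timed call. What is missing is the time in the footnote.
- *The two texts cannot both be met for FUMADERM.* Not supported. The footnote sets an upper limit, so a call at 7 weeks satisfies both. The difficulty is that much earlier or later calls also satisfy the footnote.
- *All the treatment-emergent windows rest on this call.* Not supported. The 7-day FUMADERM window does not.
- *About 13 of 55 FUMADERM subjects are affected.* This is 0.24 × 55 = 13.2, but the 24% is a discontinuation rate for adverse events that the Introduction reports from another trial. It is not a planning assumption here, and it counts everyone who stops for an adverse event, not those called early.

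What remains is that the schedule to which sites are directed contains a rule that differs from the body text. A site that follows it can shorten ascertainment without departing from the schedule.

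**Conclusion.** The inconsistency is real and is in current text. Footnote b allows a FUMADERM call anywhere up to Day +105, against about Day +49 in Sections 5.1 and 5.4.1, and states no time for risankizumab, although Section 5.4.1 does.

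Its reach is limited to early discontinuers, to the 105-day risankizumab window and the 49-day FUMADERM sensitivity window, and to the exposure denominators that use them. The primary 7-day FUMADERM window and PASI 90 at Week 24 are unaffected.

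Any loss of events assumes that a site follows the footnote rather than Section 5.4.1, calls before the relevant window closes, and receives no later spontaneous report. The documents do not allow an estimate of how many subjects that would be, or of the net direction of bias between the arms. It is worth correcting because it concerns safety follow-up after early stopping and the correction is cheap.

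**What to change.** Footnote b must be reconciled with Sections 5.1, 5.4.1 and 6.1.4, so that the schedule and the body text give one consistent call time for each arm for early discontinuers. The sponsor decides what that time is. It should then be checked against the 105-day risankizumab window and the 49-day FUMADERM sensitivity window, and against the exposure denominators in SAP 11.2.1. It cannot be asked to match every SAP window, because FUMADERM has two (7 and 49 days).

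The cost is one footnote in the next amendment and a note to sites. The analysis windows need no change on this account unless the reconciled times differ from them.
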